## FLE-002 (INSTANT) – Final Analysis

## Statistical Analysis Plan

All data will be provided in a listing, both for the MLS and PLS part of the study. For the PLS study results information is available only for subjects who started PLS study drug.

### **9.2.3.2 *Prior and concomitant medication***

In the MLS part of the trial prior and concomitant medications that were taken between 30 days of enrollment through Day 5 of the MLS part of the study is recorded by investigator. For subjects not participating in the PLS Part of the trial this Day 5 visit is the End of Study visit.

For subjects participating in the PLS trial, any additional medications are recorded up to the end of the PLS episode, being either Day 5 of the PLS study (for subject who started PLS study medication, this visit is the EOS visit for subject) or the EOS visit (for subjects who did not start PLS study medication).

All concomitant medications for the reported MLS subjects and Part C PLS subjects will be listed in the statistical report. Additionally, tables will be created to summarize the concomitant medications for the Cohorts defined Table 1 in SAP section 8. For the MLS study, in addition, tables will summarize the medication by type:

- Antiarrhythmics
- Antithrombotics
- Other cardiovascular medication
- Other medication

Additionally tables will summarize the medication by reporting all observed values (before and after start of dosing) of ATC class (e.g. B01AF=DIRECT FACTOR XA INHIBITORS) and within the specific ATC class by reporting all observed values for Standardized Medication name (e.g. Rivaroxaban, Apixaban).

### **9.2.3.3 *Treatment satisfaction for subjects meeting Primary Efficacy Endpoint***

According to protocol FLE-002 version 8.0 / EU-1 after 90 minutes post dose and prior to discharge, subjects whose AF converted to SR within 90 minutes post dose without any alternative treatment will be asked questions about their treatment satisfaction.

In the EDC for subjects who were enrolled according to an earlier version of the protocol the questions were asked after 60 minutes post dose and prior to discharge.

---

## FLE-002 (INSTANT) – Final Analysis

## Statistical Analysis Plan

---

Two questions are asked:

1. *If offered, would you take the study treatment again in the future (No/Yes)*

All results will be listed in the statistical report, in the summary tables this percentage will be reported:

$p = 100\% * (\text{Number of subjects who respond "Yes"}) / (\text{number of subjects with non-missing value})$

2. On a scale of 1 to 10, how satisfied were you with the study treatment (1 being the worst and 10 being the best)

All results will be listed in the statistical report, the summary tables include these results:

-Number of non-missing values

-Frequency and percentage of all possible outcomes (1, 2, 3, 4, 5, 6, 7, 8, 9, 10)

-Number, mean, and standard deviation of the outcomes.

Results are not available for Part C PLS.

## FLE-002 (INSTANT) – Final Analysis

## Statistical Analysis Plan

### 9.2.3.4 *Clinical laboratory evaluation analysis*

The protocol indicates:

Laboratory data are summarized by type of laboratory test. Reference ranges and clinically significant abnormal results are depicted in the summary of clinical local laboratory data, as described in the SAP. Descriptive statistics are used for each laboratory parameter at screening (Day 1) and either at 90 min after initiation of dosing or at discharge.

#### MLS

Blood samples for determination of the hematology panel, the comprehensive metabolic panel and the coagulation panel are taken at two time points:

- Approximately 45 minutes preceding initiation of drug administration
- At 90 minutes post dose (comprehensive metabolic panel only)

#### PLS

For subjects who signed IC for the PLS Part C and receive inhaled flecainide in the PLS study, blood samples are taken at one time point. Blood samples as described in Part B may be obtained on Day 1 prior to self-administration of the study drug per the discretion of the treating physician.

For all MLS cohorts, all variables shown in SAP section 6.2.5.4 for the Safety Population results will be reported shown for two time points: at screening and at 90 minutes after initiation of dosing and/or at discharge.

Comparisons will be made for changes from baseline (screening) and 90 minutes after initiation of dosing or at discharge for all parameters.

The measuring unit will be shown in all cases.

#### 1) Per Lab test characteristic (at screening, at discharge)

-Was Lab test performed (Yes/No)

Reported are: Number of analyzed subjects and the number and percentage of subjects for whom the Lab test was performed. The number of subjects for whom Lab test was performed is indicated below as: Number of subjects with Lab Test.

#### 2) Per specific test

-Was the test performed

Reported are: Number of subjects with Lab Test, and the number and percentage of subjects for whom the specific test was performed.

-If test performed: outcome is reported as follows:

#### 2.1) for Categorical characteristics

Pregnancy Test is only performed for female subjects, a Serum or Urine test can be performed, the result is categorized as “Negative” or “Positive”.

Reported are the number of female subjects for whom the overall Lab Test was performed. For these subjects the type of test (Serum/Urine) is shown by frequency and by percentage and the outcome (Negative/Positive) by frequency and percentage.

**FLE-002 (INSTANT) – Final Analysis****Statistical Analysis Plan****2.2) for Numeric characteristics**

For all other tests a numeric outcome is to be indicated in the EDC. However, investigator can also fill out “NE” as value in the EDC indicating no exact numeric value is available. The results of the test are then specified in an open text field. This option is intended to fill out test results that are Below the Limit of Quantification (BLQ), meaning in the comment field e.g., “<0.1” is reported.

In these cases in the analysis value 0 will be imputed as numeric outcome, this result will be used in the analyses described in the remainder of this section of the SAP.

For the MLS study, statistical tables will show the number of subjects in each cohort for whom the specific test was performed and the number and percentage of subjects with missing results (after performing above indicated imputation of values BLQ). For the PLS study results will only be listed.

A test can be repeated either at screening (e.g., potassium can be measured twice to confirm eligibility) or when a test failed, and a second attempt was made to measure the characteristic. If more than one non-missing value is available at screening, only the value closest to dosing (i.e., last available non-missing value) will be used in the statistical analysis.

The statistical tables will show the number of subjects in each cohort for whom specific test resulted in a numeric value, mean value and standard deviation of the numeric results are reported.

If the numeric value indicated in the EDC is lower than the Lower Limit of Normal (LLN) or higher than the Upper Limit of Normal (ULN) a question pops up in the EDC requiring investigator to fill out if the reported value is Clinically Significant (“CS”) or not (“NCS”). The statistical tables will show the number of subjects with a numeric result and the number and percentage of these subjects for whom this numeric result is classified in the EDC as Clinically Significant.

**9.2.3.5 *Protocol Deviations***

Protocol deviations will be listed, a first listing will show the Major Protocol Deviations, a second listing the minor Protocol Deviations.

In tables per cohort the Protocol Deviations will be reported:

- by category of protocol deviation (all, major, minor),
- by type of protocol deviation (e.g. Vitals, ECGs),
- by combination of category and type of protocol deviation.

**9.2.4 *Exploratory endpoints: Handheld Echo***

All HHE endpoints (refer to section 6.2.4 SAP) will be reported for the HHE population (refer to section 8.6 SAP) in listings.

This section describes the full analysis of the HHE assessments, including non-endpoints.

HHE data will be measured by investigator and filled out in the EDC. Only subjects with assessments that are normal, minimal, or absent, will be eligible for the study.

The HHE will also be submitted to an independent reviewer, at a later time, to compare with the assessments made by the site staff during the screening period. This independent review will not be used for the assessment of subject eligibility during screening.

## FLE-002 (INSTANT) – Final Analysis

## Statistical Analysis Plan

HHE echo data are not available for the PLS Part C study.

### 9.2.4.1 HHE characteristics

The report for Part C will show HHE characteristics twice: once for the results reported by investigator and once for the results reported by an independent reviewer (refer to section 5.7 SAP).

The below characteristics are reported from both reviewers:

- Was HHE performed?  
The number of subjects in the HHE population is reported as is the percentage of subjects for whom the HHE was performed. If HHE is not performed, the reasons are reported.
- LV Size  
Size is classified as “Normal” or “Enlarged”. For subjects for whom the HHE was performed, per category the number and percentages of subjects in the category is reported.  
*Enlarged is defined as: LV end-diastolic internal dimension > 55 mm for men and > 50 mm for females*
- LV-Function  
Size is classified as “Normal” or “Abnormal”. For subjects for whom the HHE was performed, per category the number and percentages of subjects in the category is reported.
- LVEF  
For the LVEF value (%) is indicated:
  - Number and percentage of subjects for whom LVEF was not evaluable
  - Number and percentage of subjects for whom LVEF was evaluable
  - Mean and standard deviation of the LVEF value (for subjects for whom LVEF was evaluable)
  - Number and percentage of subjects with a LVEF <45% (for subjects for whom LVEF was evaluable)
- LV hypertrophy  
The number and percentage of subjects is indicated for whom the HHE was performed but information on LV hypertrophy is missing.  
LV Hypertrophy is classified as “Absent”, “Mild”, “Moderate” or “Severe”. For subjects for whom the HHE was performed, and information is available, per category the number and percentages of subjects in the category is reported, as is the percentage of subjects with “Absent” or “Mild”.  
*Moderate or Severe: LV thickness > 12mm*
- Aortic Valve Disease (stenosis or regurgitation)  
The number and percentage of subjects is indicated for whom the HHE was performed but information on Aortic Valve Disease is missing.  
Aortic Valve Disease is classified as “Absent”, “Mild”, “Moderate” or “Severe”. For subjects for whom the HHE was performed, and information is available, per category the number and percentages of subjects in the category is reported, as is the percentage of subjects with “Absent” or “Mild”.

## FLE-002 (INSTANT) – Final Analysis

## Statistical Analysis Plan

- Mitral Valve Disease (stenosis or regurgitation)  
The number and percentage of subjects is indicated for whom the HHE was performed but information on Mitral Valve Disease is missing.  
  
Mitral Valve Disease is classified as “Absent”, “Mild”, “Moderate” or “Severe”. For subjects for whom the HHE was performed, and information is available per category the number and percentages of subjects in the category is reported, as is the percentage of subjects with “Absent” or “Mild”.
- Other Valve Disease (stenosis or regurgitation)  
The number and percentage of subjects is indicated for whom the HHE was performed but information on Other Valve Disease is missing.  
  
Other Valve Disease is classified as “Yes” or “No”. For subjects for whom the HHE was performed, and information is available, per category the number and percentages of subjects in the category is reported. For subjects with Other Valve Disease, a listing will specify the valve disease (as filled out in a comment field in the EDC by investigator or the comment field in the dataset from the independent reviewer).
- Other Clinically significant findings  
The number and percentage of subjects is indicated for whom the HHE was performed but information on Other Clinically significant findings is missing.  
  
Other Clinically significant findings as “Yes” or “No”. For subjects for whom the HHE was performed, and information is available, per category the number and percentages of subjects in the category is reported. For subjects with Other Clinically significant findings a listing will specify the finding (as filled out in a comment field in the EDC by investigator or the comment field in the dataset from the independent reviewer).

### **9.2.4.2 *Subject considered eligible based on HHE assessment***

Only If HHE was performed subject is included in the analysis of this endpoint.

Values are “No”, “Yes” or “Not assessable”. Per category the number and percentages of subjects in the category is reported.

Values are automatically derived in the EDC by evaluating the answers to four HHE characteristics (refer to SAP section 9.2.4.1) as indicated by investigator. For the evaluation of the results reported by the independent reviewer the same criteria will be applied in the statistical analysis.

Inclusion criteria 5 in section 4.2.B of the Protocol indicates

*If participating in the optional Handheld Echo Sub-Study, the subject must have an LVEF  $\geq$  45%, absent or mild left ventricular hypertrophy, and absent or mild valvular disease (stenosis or regurgitation) to be considered eligible for the study.*

Subject is thus considered eligible if all conditions below are applicable:

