- 6) Evidence of current ongoing myocardial ischemia, such as signs (e.g., significant [e.g., > 2 mm] ST segment elevation or depression on ECG, echocardiographic findings suggestive of acute myocardial infarction), symptoms (e.g., angina pectoris, atypical angina pectoris), and/or being medicated with anti-anginal medication. In addition, subjects with signs of prior myocardial infarction (such as pathological Q waves) who are also taking concomitant medications for angina pectoris should be evaluated for presence of ongoing ischemia.
- 7) History of myocardial infarction (MI) within 3 months of screening
- 8) Known uncorrected severe aortic or mitral valve stenosis. For subjects receiving an HHE assessment at screening (refer to exclusion criterion 5), any moderate or severe valvular disease noted during the HHE assessment is considered exclusionary.
- 9) Hypertrophic cardiomyopathy with outflow tract obstruction. For subjects receiving an HHE assessment at screening (refer to exclusion criterion 5), any moderate or severe hypertrophy noted during the HHE assessment is considered exclusionary.

Other cardiac conditions

- 10) Current diagnosis of persistent AF
- 11) One or more episodes of atrial flutter within 6 months prior to screening or atrial flutter at presentation, except subjects who received ablation for atrial flutter at least 3 months prior to screening and had no subsequent recurrence of atrial flutter prior to screening

INSTANT Study Clinical Study Protocol

Study no. FLE-002

8.0 EU-1 Version Page: 45 of 117

- 12) History of any of the following heart abnormalities:
 - a) Long QT syndrome
 - b) Conduction disease (e.g., second- or third-degree heart block, bundle branch block)
 - c) Diagnosed with sinus node dysfunction (e.g., sick sinus syndrome) and/or one of the following:
 - (i) history of unexplained or cardiovascular syncope,
 - (ii) known bradycardia suggestive of sinus node dysfunction, and/or
 - (iii) prior electrical or pharmacological cardioversion associated with prolonged sinus or ventricular pause (e.g., > 3 seconds) and/or slow ventricular rhythm (e.g., < 45 bpm) at time of conversion
 - Note: Sinus node dysfunction in AF is more prevalent in patients >75 years old.²
 - d) Brugada Syndrome
 - e) Torsades de pointes (TdP)
- 13) Any of the following ECG-related features:
 - a) QTc interval > 480 msec at screening (estimated by the Fridericia's formula¹)

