17.5 Appendix 6: Handheld Echo (HHE) Sub-Study

17.5.1 HHE Sub-Study design

Subjects who consent to participate in Part B or in the Part C Medically-Led Cardioversion Study may also consent to participate in this optional HHE Sub-Study. If they consent, they will undergo a diagnostic echocardiogram (**Figure 7**) using the Sponsor-provided portable ultrasound device. The assessments and measurements to be made from the echocardiogram are described in Section 17.5.4. Only subjects with assessments that are normal, minimal, or absent, will be eligible for the study. If the subject's HHE indicates the subject has a clinically significant enlarged LV and/or reduced EF, or clinically significant structural heart disease (e.g., LV hypertrophy, valvular disease), they will be considered ineligible for enrollment and recorded as a screen failure. The Sub-Study design is shown in **Figure 7**.

Figure 7. HHE Sub-Study Design

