17.5.3.2 HHE Sub-Study Evaluation

After providing informed consent for this Sub-Study, subjects will undergo a diagnostic echocardiogram using a Sponsor-provided handheld portable ultrasound device (HHE). The site staff will evaluate the subject's echocardiogram for any structural heart and functional abnormality. Subjects with exclusionary valvular or structural heart disease (as per exclusion criteria, refer to Section 4.2 B) or clinically significant enlarged LV or decreased EF observed on the echocardiogram will be considered ineligible for enrollment and recorded as screen failures.

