## FLE-002 (INSTANT) – Final Analysis

## Statistical Analysis Plan

- LVEF is  $\geq 45\%$
- LV hypertrophy is “Absent” or “Mild”
- Aortic Valve Disease (stenosis or regurgitation) is “Absent” or “Mild”
- Mitral Valve Disease (stenosis or regurgitation) is “Absent” or “Mild”

Subject is considered non eligible if any condition below is applicable:

- LVEF is  $< 45\%$
- LV hypertrophy is “Moderate” or “Severe”.
- Aortic Valve Disease (stenosis or regurgitation) is “Moderate” or “Severe”.
- Mitral Valve Disease (stenosis or regurgitation) is “Moderate” or “Severe”.

Subject is considered non assessable if all conditions below are applicable:

- None of the four conditions indicated in the category “non-eligible”, as indicated above, apply
- For at least one of the four characteristics used in the category “non-eligible” a missing value occurs.

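### The SAP's four-item HHE eligibility score is narrower than the protocol's HHE exclusions, and its main-reason rule relies on a criterion text that is not in protocol 4.2 B

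*SAP*

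**What the plan says.** SAP 9.2.4.2 derives HHE eligibility as yes, no or not assessable: "Values are automatically derived in the EDC by evaluating the answers to four HHE characteristics". The four are LVEF (cut-off 45%), LV hypertrophy, aortic valve disease and mitral valve disease. The independent reviewer is scored the same way: "For the evaluation of the results reported by the independent reviewer the same criteria will be applied in the statistical analysis". The not-assessable category is tied to the same list: "For at least one of the four characteristics used in the category".

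SAP 9.2.4.1 also reports LV size as normal or enlarged ("Enlarged is defined as: LV end-diastolic internal dimension > 55 mm for men and > 50 mm for females") and other valve disease as yes or no with a comment field. Neither enters the rule.

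The protocol is wider. Section 17.5.1 makes a subject ineligible for a "clinically significant enlarged LV and/or reduced EF, or clinically significant structural heart disease", and section 17.5.3.2 says subjects with "clinically significant enlarged LV or decreased EF observed on the echocardiogram will be considered ineligible for enrollment and recorded as screen failures". Exclusion 8 in section 4.2 B adds that "any moderate or severe valvular disease noted during the HHE assessment is considered exclusionary". Exclusion 9 does the same for moderate or severe hypertrophy.

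SAP 9.2.4.3 counts a subject as ineligible because of the HHE only if two conditions hold. The derived score must be ineligible, and the first failed criterion entered must be the inclusion criterion 5 cited in 9.2.4.2. SAP section 10 states accordance with V8.0 EU-1 apart from listed deviations, and this rule is not listed.

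**The concern.** The derived score is presented as eligibility, but it can differ from the eligibility that sites were told to apply. A site that correctly screen-failed a subject for a clinically significant enlarged LV, or for moderate or severe disease of a valve other than the aortic or mitral, would see that subject scored eligible whenever the four items are present and acceptable.

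The score feeds the eligibility tabulation, the count of subjects ineligible as a result of the HHE (9.2.4.3), and the table of agreement with the independent reviewer (9.2.4.5). The independent review exists to explore whether site staff assessed eligibility successfully, and no other inter-rater comparison of HHE findings is planned. A disagreement confined to an omitted item would therefore be counted as agreement.

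The source cited for the rule adds a second gap. In V8.0 EU-1, item 5 of section 4.2 B is an exclusion criterion on heart failure and LVEF, and it does not contain the text that the SAP attributes to it. HHE valve and hypertrophy findings sit under exclusions 8 and 9. A failure entered there does not satisfy the main-reason condition, even when the four-item score is ineligible.

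**Working it through.** The plan gives no figure to reproduce here, so the check compares the rules and then sizes one affected subject.

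**1. Findings side by side**

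| HHE finding | Protocol V8.0 EU-1 | Recorded (SAP 9.2.4.1) | In four-item rule | Meets main-reason condition (SAP 9.2.4.3) |
|---|---|---|---|---|
| LVEF < 45% | Exclusion 5b | Value | Yes | Yes, if criterion 5 is entered first |
| Moderate/severe hypertrophy | Exclusion 9 | Graded | Yes | No, if entered under 9 |
| Moderate/severe aortic or mitral disease | Exclusion 8 | Graded | Yes | No, if entered under 8 |
| Moderate/severe disease of another valve | Exclusion 8 | Yes/no plus comment | No | No, if entered under 8 |
| Clinically significant enlarged LV | 17.5.1 and 17.5.3.2 | Normal/enlarged | No | Unclear: not named in 4.2 B |

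**2. Truth table.** Take a subject with all four SAP items acceptable and vary the two omitted findings.

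| Clinically significant enlarged LV | Other valve moderate/severe | SAP score | Protocol |
|---|---|---|---|
| No | No | Eligible | Eligible |
| No | Yes | Eligible | Ineligible |
| Yes | No | Eligible | Ineligible |
| Yes | Yes | Eligible | Ineligible |

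The two rules differ in 3 of the 4 combinations. A missing LV size or other-valve entry cannot produce not assessable, because neither is among the four items.

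**3. Ineligible percentage.** SAP 1.3 reports six HHEs. With x ineligible of n assessable, the percentage is 100 × x/n. Exact 95% Clopper-Pearson intervals are given for scale.
- 0/6 = 0% (0 to 45.9)
- 1/6 = 16.7% (0.4 to 64.1)
- 2/6 = 33.3% (4.3 to 77.7)

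SAP 9.2.4.3 drops not-assessable subjects from the denominator, so the step is larger if any are dropped. With one dropped it is 1/5 = 20 points.

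**4. Agreement.** The first SAP 9.2.4.5 measure is 100 × (N11 + N22 + N33)/N. Suppose all six subjects are eligible for both raters under the four-item rule: 6/6 = 100%. Now score one omitted finding as ineligible.
- Both raters recorded it: N11 = 5, N22 = 1, so (5 + 1)/6 = 100%. The change is zero.
- Only one rater recorded it: N11 = 5, with one subject off the diagonal, so 5/6 = 83.3%. The change is 16.7 points.

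**The case against.** The best defence is that the four items are those with a numeric cut-off or severity grade that can be applied identically to both raters. SAP 5.6.1 says the independent reviewer does not determine clinical significance, LV size is only normal or enlarged, and other valve disease has no severity grade. This stands as a reason not simply to add the missing protocol terms for both raters: the protocol excludes a clinically significant enlargement and moderate or severe valve disease, and the fields do not carry those qualifiers. It does not justify calling the result eligibility without declaring the narrowing.

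The citation may come from a protocol version that is not available here, since SAP 1.3 refers to HHE participation under Version 7.0 EU-1 or later. The mismatch therefore does not prove a wrong source. But the SAP names V8.0 EU-1 as its basis, and even the text it cites speaks of valvular disease without naming valves.

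It is also true that LV size, other valve disease and other significant findings are reported for both raters, and that eligibility is listed per subject. With six subjects a careful reader could trace a discrepancy. That limits the harm but leaves the stated endpoint definitions wrong.

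A reader might infer that ineligible subjects have in fact been scored eligible. The documents do not support that: none of the six is reported to have an omitted finding. Nor does every LV above the SAP cut-off breach the protocol.

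**Conclusion.** The point holds as a mismatch between documents. The four-item rule can label a protocol-ineligible subject eligible, and the main-reason rule can miss HHE-based failures recorded under exclusion 8 or 9. Any misclassification is potential.

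One affected subject moves the ineligible percentage by 16.7 points if all six are assessable, and by more otherwise. A reader might carry the same figure over to agreement, but there it applies only when the raters differ on the omitted item. When both record it the change is zero.

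The conclusion rests on two readings. First, the LV-size rule stands in the EU Sub-Study appendix and not in section 4.2 B, so it clearly covers EU Sub-Study subjects but less clearly the US subjects, who are also in the HHE population. The valve criterion covers anyone receiving an HHE at screening. Second, I assume that subjects screen-failed on the HHE remain in the HHE population. SAP 8.6 defines it by consent (EU) or lack of a recent echocardiogram (US), although its last sentence speaks of enrolled subjects.

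The endpoints are exploratory, and the score does not enter the efficacy or safety analyses.

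**What to change.** - **Reconcile the sources.** Bring SAP 9.2.4.2 and 9.2.4.3 into line with protocol 4.2 B (criteria 5, 8 and 9), 17.5.1 and 17.5.3.2, and with the SAP 9.2.4 lead-in, which admits only normal, minimal or absent findings while the rule accepts mild. Cite the current protocol text. Which clinical criterion applies is for the sponsor to settle.
- **Investigator flag.** Derive it in the statistical programme from the reconciled criteria, using recorded LV size, the other-valve comment field and the recorded failed criteria.
- **Main reason.** Count HHE-based failures under criteria 5, 8 and 9, or under the Sub-Study LV-size rule, as having the HHE as main reason.
- **Agreement table.** Apply to both raters only items that both record, for example LV size as normal or enlarged, and other-valve disease classified from the comment by a documented rule.
- **Alternative.** If the four-item rule is kept, list it as a deviation in SAP section 10 and label the result a four-item score, not protocol eligibility.

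The cost is SAP wording, derived variables and a simple classification of comment fields for six subjects. No new reads are needed. The comment classification is made after the fact, so the rule should be written down before it is applied.
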